9.4.2.1.1 FIRST CO-PRIMARY ENDPOINT

The first co-primary endpoint is the change from Baseline to Week 16 in bilateral endoscopic NPS while on treatment.

Baseline endoscopic NPS is the sum of the left and right nasal polyposis score at the randomization visit. The NPS is also measured every 4 weeks during treatment and at end of treatment (Week 16). A general linear MMRM using change from baseline in NPS scores at Weeks 4, 8, 12, and 16 as response, stratification factor, treatment group as fixed effect (3 levels), treatment by stratification factor, and treatment by time interaction as fixed effects, Baseline (Day 1) NPS score as fixed continuous covariate, and subject as a random effect, will be used to obtain least squares means at EOT, to compare the etokimab treatment arms with the placebo arm.

No imputation of data for missing data due to treatment discontinuation will be implemented in the primary analysis. Comparison of the treatment arms will be based on the Week 16 least squares means of the treatment arms. An unstructured covariance matrix will be assumed and estimated in order to obtain associated standard errors for least squares means and to carry out the treatment comparisons. In case of convergence problems for the maximum likelihood estimates, other covariance structures with fewer parameters may be sought from the range of options provided in SAS PROCEDURE MIXED.

Comparison of each treatment arm with placebo will be based on the Week 16 least squares means obtained from the MMRM, where missing data due to treatment discontinuation are regarded as missing at random. Testing will be conducted in a hierarchical manner such that the comparison of the etokimab every 4 weeks treatment arm versus placebo will be conducted first. If the results of the comparison of the etokimab every 4 weeks treatment arm versus placebo are statistically significant, the etokimab every 8 weeks treatment arm will be compared to placebo. The p-value for the comparison will be obtained and compared to the significance level of 5%. An associated 2-sided 95% confidence interval will be obtained for the active minus placebo change from baseline to week 16 in the NPS for each treatment arm tested. No further adjustment will be made for testing each dosing regimen with placebo.

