In order to assess the impact of missing data due to treatment discontinuation, a sensitivity analysis may be performed where their data after dropout will be imputed using multiple imputation and the statistical analysis using MMRM will be repeated. Another sensitivity analysis may be performed where observed values of the NPS score obtained during study but after treatment discontinuation, if available, will be used. The MMRM model will be utilized where the treatment discontinuations are regarded as not missing at random (NMAR). Full details will be specified in the SAP.

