6.3.5. Efficacy Assessments

Missing data may arise due to subjects missing some assessments (intermittent missingness), or as a result of subject dropouts and not being available for subsequent assessments (monotone missingness).

The primary analysis via the general linear model with random effects (also called Mixed Model with Repeated Measures (MMRM)) uses all available data and assumes that the missing data due to dropouts are missing at random (MAR). The Kenward Roger method is used to calculate the denominator degress of freedom and adjust standard errors for the test of fixed effects. In order to assess the impact of missing data due to dropouts on the inference for the co-primary endpoints, a sensitivity analysis will be performed where data after dropout will be imputed using multiple imputation and the statistical analysis via MMRM will be repeated with the filled in data. Details on the multiple imputation is described in Section 8.1.1.3.

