8.1.1.1. Definition of Estimand

Subjects who permanently stopped the study medication are not required to withdraw from the study. Subjects were informed that if they decided to discontinue study medication, they had the option of providing clinic assessments at scheduled office visits or by phone contact until the planned end of their study visits.

Thus, the (co)primary estimand chosen here is the de facto or treatment policy estimand, which uses the available on-treatment NPS values during Treatment period. The primary time point is Week 16.

The NPS is also measured every 4 weeks during treatment and at end of treatment (Week 16). A general linear mixed model with repeated measures (MMRM) will be used to obtain least squares means of change in NPS at Week 16 from baseline, to compare the etokimab treatment arms with the placebo arm.

Summary statistics for each time point will include n, mean, standard deviation, median, minimum, and maximum, for baseline, each time of measurement, and the change from baseline calculated as post-baseline value minus the baseline value.

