8.1.1.3. Supplementary Statistical Analysis for NPS

In order to assess the impact of missing data due to dropouts on the inference for the co-primary endpoints, a sensitivity analysis will be performed in 2 ways. First, NPS data after dropout will be imputed using multiple imputation and the statistical analysis using MMRM will be repeated. Multiple imputation analyses will be performed based on both Missing at Random (i.e. the missing data are assumed to follow the same model as the other patients in their respective treatment arm) and Missing Not at Random assumptions. Second, an ANCOVA will be performed only for the subjects who have completed Week 16 assessment (ie., completers analysis).

MI analysis with Missing at Random (MAR) assumption: In the analysis of each of the co-primary endpoints, subjects with missing data at post-baseline visits will have data imputed using multiple imputation (MI) methodology using the total study sample. MI will be performed under the assumption of MAR. Intermittent missing value(s) will also be replaced using MI. MI will impute 10 integer values using Markov Chain Monte Carlo (MCMC) methods assuming nonmonotone missing, a pre-specified seed number, 500 burn-in iterations, 100 iterations between imputations, and a non-informative prior. The imputation models based on all subjects (regardless of treatment group) will include the randomization stratification factor, the baseline value of the endpoint, and all previous values of the endpoint at each time point. Results from the analysis of each of the 10 imputed datasets will be combined using Rubin's imputation rules (Rubin 1987) to produce a pooled least squares mean (LSM) estimate of treatment difference. **MI analysis with Missing Not at Random (MNAR) assumption (placebo-based):** A placebo-based multiple imputation will be performed using a pattern mixture model under the assumption of MNAR for each coprimary endpoints. For these analyses, the imputation model will be estimated using placebo subjects only. The imputation models will include the randomization stratification factor, the baseline value of the endpoint, and all previous values of the endpoint at each time point. See Ratitch and O'Kelly (2011) for additional details regarding the methodology used to obtain the placebo-based imputation datasets. Similar methods as described for the previous multiple imputation method will be used to produce a pooled LSM estimate of treatment difference.

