8.1.2.1. Definition of Estimand

The SNOT-22 is measured every 4 weeks during treatment and at end of treatment (Week 16). The primary time point is Week 16. A general linear MMRM using the change from baseline in SNOT-22 scores at Weeks 4, 8, 12, and 16 as response; baseline (Day 1) SNOT-22 score as fixed covariate; treatment group, randomization stratification factor, time (Weeks 4, 8, 12, and 16), and treatment by time interaction as fixed effect; and subject as a random effect will be used to obtain least squares means to compare the etokimab treatment arms with the placebo arm.

Summary statistics for each time point will include n, mean, standard deviation, median, minimum, and maximum, for baseline, each time of measurement, and the change from baseline calculated as post baseline value minus the baseline value.

Subjects are also asked to choose the maximum of 5 most important items that are affecting their health at each SNOT-22 assessment. A summary table for each time point will be provided including the frequency and percentage of each item chosen as the top 5 items.

8.1.2.2. *Primary Statistical Analysis for SNOT-22*

The (co)primary hypothesis to be tested for this estimand is that treatment of adults diagnosed with CRSwNP using etokimab will result in a significantly greater reduction of Week 16 SNOT-22 from baseline when compared to placebo. This hypothesis will be tested by comparing the least squares adjusted means for each etokimab dose group with placebo, at the Week 16 time point. Comparison of each treatment arm with placebo will be based on the Week 16 least squares means obtained from the MMRM, where missing data due to dropouts are regarded as missing at random (MAR). The same procedure employed to NPS will be repeated for the primary statistical analysis of SNOT-22.

Graphical displays of the results will be presented. The (by time-point) least squares means and two-sided 95% confidence intervals for each treatment depicted with error bars will be plotted against time, and the p-values for the Week 16 comparisons will be displayed on the Week 16 time point.

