10.1. Extent of Exposure

Etokimab is administered subcutaneously. The predicted etokimab half-life is approximately 14 days. The PK data generated to date indicate that a linear PK profile is observed upon etokimab administration regardless of the route. Hence, for the sake of calculating duration of treatment exposure in this study, we will assume that a subject's exposure to study medication continues up to 28 days after SC injection. Thus, duration of total exposure will be calculated per subject as follows:

Duration of total exposure = (Date of last dose of study medication +28) – Date of first dose of study medication +1

Duration of total exposure and total drug administered will be summarized by treatment group for the Safety Analysis Set using n, mean, standard deviation, minimum, Q_1 , median, Q_3 and maximum. Study drug administration per visit will be listed for the SAF.

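### The SAP labels the co-primary estimand treatment policy but ties it to on-treatment values, and two date rules (Treatment Period end, last-dose visit windowing) need correcting

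*SAP*

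**What the plan says.** **Estimand and data.** SAP 8.1.1.1 first notes that "Subjects who permanently stopped the study medication are not required to withdraw from the study" and then concludes that "the (co)primary estimand chosen here is the de facto or treatment policy estimand, which uses the available on-treatment NPS values during Treatment period". Protocol 9.4.2.1.1 reads: "The first co-primary endpoint is the change from Baseline to Week 16 in bilateral endoscopic NPS while on treatment". It treats data missing because of treatment discontinuation as missing at random (MAR). SAP 6.3.5 says that the primary analysis "uses all available data and assumes that the missing data due to dropouts are missing at random (MAR"). The PROC MIXED code in SAP 8.1.1.2 has no treatment-status filter.

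**SNOT-22.** SAP 8.1.2.1 names no estimand strategy. SAP 8.1.2.2 adds only this: "The same procedure employed to NPS will be repeated for the primary statistical analysis of SNOT-22".

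**Off-treatment values.** Protocol 7.1 encourages subjects who stop study drug to attend their remaining visits, and Protocol 9.4.2.3 expects their assessments to support sensitivity analyses of the co-primaries. Protocol 9.4.2.1.1 offers an optional analysis in which "observed values of the NPS score obtained during study but after treatment discontinuation, if available, will be used"; Protocol 9.4.2.1.2 does the same for SNOT-22. SAP 8.1.1.3 says that "a sensitivity analysis will be performed in 2 ways": multiple imputation (MAR and placebo-based), and an ANCOVA in Week 16 completers. SAP 8.1.2.3 repeats these for SNOT-22. SAP section 12 records only a change to nocturnal awakenings.

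**Dates.** SAP 6.2.3 ends the Treatment Period one day before Visit 7/EOT and starts Safety Follow-up on the Visit 7 date; SAP section 8 limits primary and secondary efficacy to Treatment Period data. SAP 6.4 maps unscheduled, EOT and ET visits by study day from first dose. Its next rule places unscheduled visits dated after EOT, ET visits among them, by days since last dose, using the same tables.

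**The concern.** A reader of the SAP cannot tell which values enter the primary MMRM for a subject who stops injections and keeps attending. If they are left out and the model projects to Week 16 under MAR, the target is hypothetical: the effect had treatment continued. If they are kept, the target is treatment policy. Two competent programmers could build different co-primary datasets, and a report could carry a treatment-policy label that its data do not support.

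Placebo-based imputation assumes what happens after stopping. Values observed after stopping would show it, and the one MMRM designed to use them was not carried into the SAP.

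The two date rules matter because, followed literally, one excludes the primary visit and the other files follow-up assessments of NPS and SNOT-22 at earlier treatment visits.

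**Working it through.** **The plan's own figures (SAP 3.6).** Power = Φ(Δ / (SD√(2/n)) − 1.96), with n = 27 per arm.
- NPS: Δ 1.3, SD 1.5 gives 0.890 (0.878 by noncentral t); the plan says about 87%.
- SNOT-22: Δ 18.1, SD 19.2 gives 0.934 (0.925 by noncentral t); the plan says 92%.
- 27 / 0.82 = 32.9, so 33 per arm; 0.87 × 0.92 = 0.80 joint power.

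All reproduce, and none is in dispute.

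**(a) Which values enter.**

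| Source | Points to |
|---|---|
| Protocol 9.4.2.1.1 | On-treatment values, MAR after treatment discontinuation |
| SAP 8.1.1.1, data rule | On-treatment values |
| SAP 8.1.1.1, label and the reason given for it | Values regardless of stopping |
| SAP 6.3.5 | Everything observed; missingness tied to dropouts |
| SAP 8.1.1.2, code | No filter |
| SAP 8.1.2.1 (SNOT-22) | No strategy stated |

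Neither document defines on-treatment for efficacy.

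**(b) Treatment Period.** The period's last day is the Visit 7 date − 1. A value dated at Visit 7 is therefore one day outside it, and section 8 would exclude it. Against this, Table 2a lists Week 16 (Days 99–126) under the Treatment Period, SAP 8.1.1 counts Week 16 among the treatment visits, and the model includes Week 16. Week 16 is plainly meant to count.

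**(c) Visit windows.** Table 2a, counted from first dose: Week 4 = Days 2–42, Week 8 = 43–70, Week 12 = 71–98, Week 16 = 99–126, Week 24 = 127–182. Take the last dose on Day 85 and an unscheduled or ET visit after EOT:

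| Visit day | From first dose | Days since last dose | From last dose |
|---|---|---|---|
| 141 | Week 24 | 141 − 85 = 56 | Week 8 |
| 169 | Week 24 | 169 − 85 = 84 | Week 12 |

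Counting the dose day as day 1 (57 and 85) changes neither result. In SAP 6.4 a scheduled record outranks other records in its window, so the misfiled value enters the MMRM only where the scheduled Week 8 or Week 12 record is missing.

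If the last-dose rule is read to cover early stoppers too: Protocol 7.1 asks for an ETV within 30 days of last dose. After a Day 85 dose, an ETV on Days 99–115 is 14–30 days after the dose, so it is Week 16 from first dose but Week 4 from last dose.

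**Size (illustration only).** Let s be the share per arm who stop and are still observed at Week 16, and r the share of benefit they retain, with the placebo mean unaffected by stopping. The treatment-policy difference is then smaller than the on-treatment one by s(1 − r)Δ. The documents give neither s nor r. Assume s runs from 0 to 0.18 (the plan's allowance for dropouts and missing data, so probably high here) and r from 1 to 0.
- NPS: 0 to 0.18 × 1.3 = 0.23 points. SE = 1.5√(2/33) = 0.369, so 0 to 0.63 SE.
- SNOT-22: 0 to 0.18 × 18.1 = 3.3 points. SE = 19.2√(2/33) = 4.73, so 0 to 0.69 SE.

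**The case against.** The strongest reply is that the SAP follows study participation throughout. Its reason for the label, the wording in 6.3.5, the attribution of missingness to dropouts and the unfiltered code all fit treatment policy, and on-treatment may simply mean the 16-week period. This stands far enough to defeat one inference: that the label alone is wrong and the SAP analyses only on-treatment values. The documents conflict; they do not settle it. Protocol 9.4.2.1.1 still points the other way, so reconciliation is needed.

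A reader might also infer that no planned analysis uses off-treatment values. The documents do not support that. The completers ANCOVA (SAP 8.1.1.3) and the responder analyses (SAP 8.2.2, 8.2.3) have no treatment-status filter and may include some. They do not replace an MMRM on all observed values.

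A reader might take SAP 10.1, under which "exposure to study medication continues up to 28 days after SC injection", as the on-treatment cut-off and test the plan against it. That convention is stated only for calculating duration of exposure; nobody proposes it for efficacy.

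On 6.4, the more natural reading confines the last-dose rule to visits after EOT. A subject with no Visit 7 has no EOT date to be after, so the first-dose rule applies and the Day 99–115 example falls away. That is fair, but the Day 141 and Day 169 misfiling remains on that reading.

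Finally, the protocol makes the off-treatment MMRM optional, and the SAP already plans MAR and placebo-based imputation. True, but Protocol 9.4.2.3 anticipates using these data, and section 12 does not record the omission.

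**Conclusion.** The point holds as a set of contradictions to resolve before unblinding. The treatment-policy label and the on-treatment data rule cannot both stand, the documents disagree on which was meant, and SNOT-22 has no strategy of its own. The Treatment Period end date is a boundary slip; a reader might infer that Week 16 is excluded from the primary analysis, but Table 2a, SAP 8.1.1 and the model show otherwise. The last-dose rule misfiles post-EOT unscheduled and ET visits even on its narrow reading, and reaches the primary model only where a scheduled record is missing.

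The effect on the co-primary result is unknown and may be zero. The ranges of 0 to 0.23 NPS points and 0 to 3.3 SNOT-22 points rest on assumed values of s and r and do not estimate bias. The usable share may be well below 18%: Protocol 6.5.1 removes subjects given systemic rescue from the study, and SAP 8.1.1.1 allows contact by phone, which cannot yield an endoscopic score.

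**What to change.** 1. **SAP 8.1.1.1 and 8.1.2.1.** Choose one strategy for both co-primaries, and make label and data agree with SAP 6.3.5 and Protocol 9.4.2.1.1.
   - *Hypothetical:* exclude values after permanent treatment discontinuation, under one analysis rule that is the same in every arm and keeps the Week 16 visit of subjects who completed dosing. In 8.1.1.3 and 8.1.2.3, add one sensitivity MMRM per co-primary on all observed values through the Week 16 window.
   - *Treatment policy:* use all observed values through the Week 16 window regardless of treatment status, reconcile the protocol's endpoint wording, and record the change in section 12.
2. **SAP 6.2.3.** End the Treatment Period on the Visit 7/EOT date inclusive and start Safety Follow-up the next day.
3. **SAP 6.4.** Delete the last-dose rule and window all ET and unscheduled visits by study day from first dose. Table 2a already runs without gaps to Day 182.

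The cost is SAP wording and, under the hypothetical strategy, one extra MMRM per co-primary. No new data are needed. The estimate that includes off-treatment values may be less favourable.

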8.1.1.2. Primary Statistical Analysis for NPS

Statistical analysis of this endpoint will employ a general linear model with repeated measures (also called a mixed model with repeated measures, MMRM), with the change from baseline in NPS as the dependent variable; baseline (Day 1) NPS score as a covariate, treatment group (3 levels), stratification factor, treatment by stratification factor, categorical time points (Weeks 4, 8, 12 and 16) and treatment by time interaction as fixed effect factors, and subject as a random effect in the model. Assuming treatment (trtpn) is coded as Placebo=1, Eto Q8W=2, Eto Q4W=3, and that the time variable (weekn) is ordered as 4, 8, 12, and 16, we can write the SAS model of interest to be performed with SAS PROCEDURE MIXED as follows:

```
PROC MIXED DATA = DATASETNAME;
CLASS USUBJID WEEKN TRTPN STRAT;
MODEL CFB = BASE STRAT TRTPN STRAT*TRTPN WEEKN WEEKN*TRTPN / SOLUTION DDFM=KR;
REPEATED WEEKN / SUBJECT=USUBJID TYPE=UN;
LSMEANS WEEKN*TRTPN / CL ALPHA=0.05;
RUN;
```

The (co)primary hypothesis to be tested for this estimand is that treatment of adults diagnosed with CRSwNP using etokimab will result in a significantly greater reduction of Week 16 NPS from baseline when compared to placebo.

This hypothesis will be tested by comparing the least squares adjusted means for each etokimab dose group with placebo, at the week 16 time point. Comparison of each treatment arm with placebo will be based on the change in least squares means at Week 16 obtained from the MMRM. Testing will be conducted in a hierarchical manner such that the comparison of the etokimab Q4W treatment arm versus placebo will be conducted first.

If the results of the comparison of the eetokimab Q4W treatment arm versus placebo are statistically significant, the etokimab Q8W treatment arm will be compared to placebo.

While the treatment group means at each visit are estimated by the model, the standard deviations are nuisance parameters and must also be estimated in order to carry out the hypothesis tests and/or obtain confidence interval estimates for means and contrasts. An unstructured covariance matrix will be assumed and estimated in order to obtain associated standard errors for least squares means and to carry out the treatment comparisons. In case the model does not converge with the unstructured covariance structure, the heterogeneous Toeplitz structure (TOEPH) will be used instead. In case the model will not converge with the heterogeneous Toeplitz structure, heterogeneous compound symmetry (CSH) will be used instead. The denominator degrees of freedom will be computed using the Kenward-Roger method.

The p-value for the comparison will be obtained and compared to the significance level of 5%, two-sided. An associated 2-sided 95% confidence interval will be obtained for the active minus placebo change from baseline to week 16 in the NPS for each treatment arm tested. Comparison of multiple treatment groups versus placebo will be performed in a hierarchical manner so further adjustment will not be made for testing each dosing regimen with placebo. Statistical significance (two-sided p-value < 0.05) for a treatment contrast will be taken to infer a difference in efficacy versus placebo for that etokimab dosing regimen. The direction of difference will determine whether that dosing regimen of etokimab is better or worse than the placebo group at that specified level of significance.

Graphical displays of the results will be presented. The (by-time point) least squares means and two-sided 95% confidence intervals for each treatment will be plotted against time, and the p-values for the Week 16 comparisons will be displayed on the Week 16 time point.

8.1.1.3. Supplementary Statistical Analysis for NPS

In order to assess the impact of missing data due to dropouts on the inference for the co-primary endpoints, a sensitivity analysis will be performed in 2 ways. First, NPS data after dropout will be imputed using multiple imputation and the statistical analysis using MMRM will be repeated. Multiple imputation analyses will be performed based on both Missing at Random (i.e. the missing data are assumed to follow the same model as the other patients in their respective treatment arm) and Missing Not at Random assumptions. Second, an ANCOVA will be performed only for the subjects who have completed Week 16 assessment (ie., completers analysis).

MI analysis with Missing at Random (MAR) assumption: In the analysis of each of the co-primary endpoints, subjects with missing data at post-baseline visits will have data imputed using multiple imputation (MI) methodology using the total study sample. MI will be performed under the assumption of MAR. Intermittent missing value(s) will also be replaced using MI. MI will impute 10 integer values using Markov Chain Monte Carlo (MCMC) methods assuming nonmonotone missing, a pre-specified seed number, 500 burn-in iterations, 100 iterations between imputations, and a non-informative prior. The imputation models based on all subjects (regardless of treatment group) will include the randomization stratification factor, the baseline value of the endpoint, and all previous values of the endpoint at each time point. Results from the analysis of each of the 10 imputed datasets will be combined using Rubin's imputation rules (Rubin 1987) to produce a pooled least squares mean (LSM) estimate of treatment difference. **MI analysis with Missing Not at Random (MNAR) assumption (placebo-based):** A placebo-based multiple imputation will be performed using a pattern mixture model under the assumption of MNAR for each coprimary endpoints. For these analyses, the imputation model will be estimated using placebo subjects only. The imputation models will include the randomization stratification factor, the baseline value of the endpoint, and all previous values of the endpoint at each time point. See Ratitch and O'Kelly (2011) for additional details regarding the methodology used to obtain the placebo-based imputation datasets. Similar methods as described for the previous multiple imputation method will be used to produce a pooled LSM estimate of treatment difference.

Completers analysis: An Analysis of Covariance (ANCOVA) will be employed for Week 16 NPS for subjects who completed Week 16 only, where the change from baseline at Week 16 is modeled with baseline NPS score as covariate and treatment as a factor.

All primary and supplementary statistical analyses will be performed for the Full Analysis Set. If the Full Analysis Set and the Per Protocol Analysis Set differ by more than 10 subjects, the primary analysis of NPS will be repeated for the Per Protocol Analysis Set.

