3.6. Determination of Sample Size

The two co-primary endpoints were assessed in order to determine the sample size that will provide adequate power to detect a clinically meaningful difference between each etokimab dosing regimen and placebo.

Sample size estimates were calculated based on the following assumptions:

- Overall alpha=0.05
- Co-primary endpoints
- Hierarchical testing of the 2 active treatment arms versus placebo

Based on data from similar trials conducted in adult subjects with CRSwNP, a difference in NPS of 1.3 between the etokimab change from baseline to week 16 and the placebo group change from baseline to week 16 will be clinically meaningful (*Bachert et al. 2016*). Assuming a standard deviation of 1.5, and a significance level of 5%, a sample size of n=27 for each treatment arm will provide approximately 87% power to detect the stipulated difference. In order to account for the dilution of treatment effect due to 18% dropouts and missing data, approximately 33 subjects are planned to be randomized equally to each of the three treatment arms.

The second co-primary endpoint is SNOT-22 total score. In a trial of adults with CRSwNP, the difference in mean change from baseline to Week 16 between active and placebo was 18.1. Assuming a common standard deviation of 19.2, and 2-sided significance level of 5%, the sample size of 27 subjects provides 92% power to detect the stipulated treatment difference. Hence, adjusting for 18% dropouts and missing data, n=33 subjects will provide >85% desired power to detect a clinically meaningful difference in this endpoint between each active arm and placebo.

Each co-primary endpoint will will be tested against two-sided alpha=0.05; therefore, the combined power for the testing of both endpoints is approximately 80%, assuming no negative correlation between endpoints.

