5.3. Full Analysis Set

The Full Analysis Set (FAS) will include all randomized subjects who receive at least 1 dose of etokimab or placebo and have baseline and at least 1 post baseline NPS and/or SNOT-22 scores up to Week 16. Subjects will be analyzed according to randomized treatment. Unless specified otherwise, this set will be also used for subject listings and summaries for all efficacy analyses.

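### SAP 8.1.1.3 defines MAR by treatment arm but imputes from a pooled model with no treatment term, so the supplementary MAR difference is usually pulled toward zero

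*SAP*

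**What the plan says.** SAP 8.1.1.3 opens by explaining MAR as arm-specific: "the missing data are assumed to follow the same model as the other patients in their respective treatment arm". The paragraph that specifies the MAR imputation then describes a pooled procedure twice. Subjects with missing post-baseline data "will have data imputed using multiple imputation (MI) methodology using the total study sample", and "The imputation models based on all subjects (regardless of treatment group) will include the randomization stratification factor, the baseline value of the endpoint". The only other listed term is the set of earlier values of the same endpoint.

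The MNAR paragraph that follows is clear about its own source of information: "For these analyses, the imputation model will be estimated using placebo subjects only".

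The imputed data are then analysed with the primary MMRM of SAP 8.1.1.2, whose fixed effects are "MODEL CFB = BASE STRAT TRTPN STRAT*TRTPN WEEKN WEEKN*TRTPN".

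SAP 8.1.2.3 applies the same supplementary analyses to SNOT-22. Nothing elsewhere settles the conflict: SAP 6.3.5 refers to 8.1.1.3 for the details, and Protocol 9.4.2.1.1 and 9.4.2.1.2 leave them to the SAP.

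**The concern.** The analysis model estimates treatment, treatment by time and treatment by stratum; the imputation model contains none of them. Treatment can influence an imputed value only through the subject's own other observed scores, which for a dropout means the earlier ones. Those scores carry only part of the Week 16 effect. Active dropouts are therefore imputed partly toward placebo and placebo dropouts partly toward active.

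The primary MMRM is already an MAR analysis (SAP 6.3.5), so a correct MAR imputation should nearly reproduce it. The placebo-based result can then be read as the effect of changing the missing-data assumption. As written, the result labelled MAR moves because of its own model, and a reader could take that movement for sensitivity to dropout. With similar dropout across arms it nearly coincides with the placebo-based result. With heavier placebo dropout it is usually the more attenuated of the two. Unequal dropout is possible: under SAP 8.3.10, subjects given systemic rescue leave the study.

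**Working it through.** **Inputs from SAP 3.6.** NPS difference 1.3, SD 1.5; SNOT-22 difference 18.1, SD 19.2; 27 per arm; 18% dropout and missing data (a planning figure, not a cap).

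**The plan's own figures.** The SAP gives none for the imputation itself, so I checked the planning inputs.
- NPS: 1.3 / (1.5 × √(2/27)) = 3.18. Power is Φ(3.18 − 1.96) ≈ 89.0% by normal approximation and 87.8% by noncentral t; the SAP states 87%.
- SNOT-22: 93.4% and 92.5%; the SAP states 92%.
- Sample size: 27 / (1 − 0.18) = 32.9, so 33. The inputs reproduce.

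**Assumptions not in the documents.** Equal correlation between visits of 0.3, 0.5 or 0.7; the same effect in both active arms; dropout unrelated to outcome; Week 4 always observed; dropout either all after Week 4 or spread over Weeks 4 to 12. Effect at Weeks 4/8/12/16 as a share of Week 16: building 0.5/0.67/0.83/1, stable 1/1/1/1, waning 1.5/1.4/1.2/1. Two unequal splits were added, both averaging 18%: (34+10+10)/3 and (10+22+22)/3.

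**Large-sample result, NPS, true difference 1.30** (sequential regression imputation, 300,000 per arm):

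| Dropout placebo / active | Scenario | Pooled, as written | By arm | Placebo-based |
|---|---|---|---|---|
| 18% / 18% | building, 0.3, after Week 4 | 1.108 | 1.299 | 1.101 |
| 18% / 18% | stable, 0.7, spread | 1.259 | 1.299 | 1.250 |
| 18% / 18% | waning, 0.7, spread | 1.323 | 1.301 | 1.332 |
| 34% / 10% | building, 0.3, after Week 4 | 1.005 | 1.297 | 1.182 |
| 34% / 10% | stable, 0.7, spread | 1.239 | 1.300 | 1.273 |
| 10% / 22% | building, 0.3, after Week 4 | 1.149 | 1.301 | 1.057 |
| 10% / 22% | stable, 0.7, spread | 1.272 | 1.304 | 1.245 |

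For equal dropout the shortfall is 1 − 1.108/1.30 = 15% at most and 1 − 1.259/1.30 = 3% at least. Over the waning scenarios with equal dropout the pooled estimate runs from 1.21 to 1.32. For SNOT-22 (true 18.1, stable or building) the pooled ranges for the three splits, in table order, are 15.4 to 17.6, 14.1 to 17.3 and 15.9 to 17.7.

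**Bounding case: no earlier post-baseline value.** SAP 5.3 admits subjects who "have baseline and at least 1 post baseline NPS and/or SNOT-22 scores up to Week 16", so someone can enter with no post-baseline NPS. If every missing subject were like this, each would be imputed at the pooled observed mean. With dropout dP (placebo) and dA (active), the observed active share is w = 2(1 − dA) / [2(1 − dA) + 1 − dP], and the pooled difference is δ × [(1 − dA) − (dP − dA) × w].
- 18/18: 1.3 × 0.82 = 1.07.
- 34/10: w = 1.80/2.46 = 0.732; 1.3 × (0.90 − 0.24 × 0.732) = 0.94.
- 10/22: w = 1.56/2.46 = 0.634; 1.3 × (0.78 + 0.12 × 0.634) = 1.11.

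**Wider grid.** In 96 scenarios with 18% dropout (two correlation structures, correlation 0.3 to 0.9, four time-courses, three dropout timings), pooled was below by-arm in 88. In all 72 with a constant or building effect, the ratio of pooled to by-arm was 0.82 to 0.99. The 8 exceptions (1.00 to 1.04) all combined a waning effect with correlation 0.7 or 0.9.

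**At trial size** (33 per arm, 10 imputations, 1,500 trials, equal 18% spread dropout, correlation 0.5, stable effect):

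| Imputation model | Mean | Rubin SE | Empirical SD |
|---|---|---|---|
| Pooled, as written | 1.22 | 0.402 | 0.356 |
| By arm | 1.30 | 0.419 | 0.400 |
| Pooled with treatment and treatment by stratum | 1.30 | 0.405 | 0.396 |

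The pooled standard error is also about 13% too large (0.402/0.356 = 1.13). In a further 600 trials per setting with a linear build-up, pooled gave 1.13 against 1.30 with a treatment term, and power of about 80% against 89%. With a constant effect the power was almost the same (88% for both).

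**The case against.** The strongest reply is about reach and realism. This is one of three supplementary analyses. The MMRM, testing hierarchy, alpha and sample size do not depend on it, and the placebo-based result can be compared directly with the primary. That is right, and it caps the importance of the point.

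The scenarios can also be challenged:
- **Unequal splits.** They are assumed, and rescue-driven dropout would relate to outcome. When dropout was made to depend on the Week 4 score, pooled still gave 1.10 to 1.14 against 1.30 to 1.31 by arm.
- **No earlier value.** NPS and SNOT-22 share their visits, so this should be uncommon. It is a bound, not an expectation.
- **Early-termination visits.** They supply scores that are mapped to analysis windows (SAP 6.4). One extra visit per dropout narrows the equal-dropout range to about 1.15 to 1.28, in the same direction.
- **Imputation details.** The SAP's nonmonotone MCMC lets later scores inform intermittent gaps, and it imputes integers. Neither was modelled.
- **Waning effect.** The sign can reverse. When baseline was given the same correlation as the visits, the one waning case run gave 1.28 and the reversal disappeared; the stable case fell from 1.26 to 1.23.

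Finally, pooling is not plainly worse as an estimator. At trial size its root mean squared error is √(0.08² + 0.356²) = 0.365 against 0.400 by arm, and estimate over standard error is 3.03 against 3.10. That does not cure the mislabelling: the output would be called MAR without following the SAP's definition, and the SAP already has an intentionally conservative analysis.

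**Conclusion.** The concern holds. The contradiction is explicit, and a programmer following the operative wording would not produce the analysis the section defines. With 18% dropout in each arm and a stable or building effect, the supplementary NPS difference comes out 3% to 15% low (1.11 to 1.26 of 1.30), within 0.01 to 0.03 of the placebo-based result. The 34%/10% split gives 1.01 to 1.24 against 1.18 to 1.27 placebo-based; the 10%/22% split gives 1.15 to 1.27 against 1.06 to 1.25. By-arm imputation returns 1.29 to 1.31 throughout. The size rests on the assumed correlations, time-courses and dropout splits, and a waning effect can remove or reverse the pull. The harm is confined to interpreting the sensitivity analyses of both co-primary endpoints. It should be corrected before unblinding.

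**What to change.** In the MAR paragraph of SAP 8.1.1.3, replace both pooled phrases (the one on the total sample and the one on all subjects regardless of arm) with imputation run separately within each treatment arm. This matches the section's own definition and carries to SNOT-22 through 8.1.2.3. Leave the placebo-based analysis unchanged.

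State a fallback for unstable MCMC at about 33 per arm: a pooled model that includes treatment group and treatment by stratum. Define what counts as unstable in advance, so that the choice does not depend on the results. Adopting that pooled model from the start would also remove the bias.

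Cost: two phrases in one paragraph and one statement in the imputation code. By-arm imputation has less stable parameters, with a standard error about 3% larger than the pooled model with treatment terms (0.419/0.405 = 1.03).
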